1. INTRODUCTION

1.1 Background

For at least 2 decades low-dose acetylsalicylic acid (LDA) has been used for the prevention of thromboembolic events. The dose range of LDA is 75 to 325 mg daily. The individual doses for different indications vary between countries. The antithrombotic effect of LDA seems to be similar within the dose range of 75 to 325 mg daily (Patrono C et al 2005).

Continuous low-dose ASA treatment is accompanied by a variety of undesirable AEs. These include upper gastrointestinal (GI) symptoms such as dyspeptic symptoms, abdominal pain and/or heartburn (Silagy CA et al 1993, Laheij RFJ et al 2003), peptic ulcers which might be followed by serious ulcer complications such as bleeding, gastric or duodenal perforation and obstruction (Lanas A et al 2006, Yeomans ND et al 2005, García Rodríguez LA and Hernández-Díaz S 2004, CAPRIE Steering Committee 1996, Weil J et al 1995). Even taking ASA in doses as low as 75 mg daily significantly increases the risk of having symptomatic peptic ulcer as well as the risk of having upper GI bleeding compared with not taking aspirin (García Rodríguez LA and Hernández-Díaz S 2004, Weil J et al 1995, Laine L 2006).

While the risk, nature, and development of ulcer and ulcer complications associated with LDA treatment is well documented, less is known about upper GI symptoms. The nature, occurrence rate, and impact of upper GI symptoms associated with LDA treatment, as well as these symptoms' potential influence on compliance with LDA treatment, use of acid inhibitory drugs and other medications is the focus of the current study.

To understand how symptoms develop and are experienced, it is best to ask the subjects themselves (i.e. a patient reported outcome, PRO). Further it is important to understand these symptoms in a non-interventional, naturalistic environment. As such any methodology used needs to be aimed at observing, rather than influencing, the symptoms of interest. Historically, cross-sectional PRO surveys and face-to-face interviews have been used to evaluate subjects symptoms and disease experience. While useful for understanding the subjects' global perspective on their condition, retrospective recall is known to be problematic for documentation of the subjects' day-to-day experience.

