an electronic PRO device (ePRO) to record information about their experience with LDA for the period of 3 months. The ePRO device will prompt (via an audible alarm) the subject three (3) times each day and administer questions regarding the subject's experience with LDA. In particular, the ePRO device will ask subjects about UGI symptoms, medication use, and about their daily activities and mood. The areas of assessment are listed in Section 4.2.1 (Table 2), and the specific questions are listed in Appendix D. The goal is to obtain EMA data from 350 subjects in the three groups: 200 Naïve LDA users (240 enrolled) who begin LDA use at the time of the study; 100 Short-term LDA users (120 enrolled); and, 50 Long-term LDA users (60 enrolled). A detailed description of the inclusion/exclusion criteria for each EMA group can be found in Section 3.3.3.

Finally, a sample of up to 20 subjects from the three EMA groups will be interviewed (see Section 3.3.4) to further debrief their experience with LDA and upper GI symptoms. This 1 hour cognitive interview will include the following areas:

- the subject's experience with upper GI symptoms;
- the subject's use of and compliance with LDA and other CV related medication;
- the subject's perceived impact of upper GI symptoms on their ability to continue with medication;
- the broader impact of these symptoms on their life.

The subjects will be selected following review of Diary/EMA data, and investigators will be asked to invite selected subjects to participate in these interviews.

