4.2.2 EMA assessments (stage 2)

The areas that will be assessed in the Diary/EMA phase utilizing the ePRO device are outlined below and listed in detail in Appendix D.

Table 3 ePRO-EMA Diary Variables by Daily Measurement Time

Time point Measurement	Morning AM	Afternoon PM	Evening ER	Self-initiated SI
Sleep	X			
Mood	X	X	X	X
Activities	X	X	X	X
Eating/food	X	X	X	X
GI symptoms	X*	X*	X*	X
GI coping strategies	X*	X*	X*	X
Medication usage	X	X	X	X
Healthcare Utilization			X	

* If subject reported elevated symptoms on a screening question, then they would receive all GI symptoms similar to debriefing of a SI episode.

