1. SITEPRO CROSS-SECTIONAL SURVEY ITEMS AND QUESTIONNAIRES

Text	Response options
What is your gender?	Female, Male
Please answer the following questions about gastrointestinal symptoms (GI)	
GI symptoms relate to the stomach and intestines, and include indigestion, abdominal pain and/or heartburn.	
Have you experienced any GI symptoms in the past year?	Yes, No
Did you experience the symptoms only during pregnancy?	Yes, No, Not Applicable
Have you experienced any GI symptoms in the past 14 days?	Yes, No
Thinking about your symptoms over the past 14 days, how often did you have the following:	Yes, No
A burning feeling behind your breastbone?	Yes, No
Pain behind your breastbone?	Yes, No
A burning feeling in the center of the upper stomach?	Yes, No
A pain in the center of the upper stomach?	Yes, No
An acid taste in your mouth?	Yes, No
Unpleasant movement of material upwards from the stomach?	Yes, No

Have you taken PPIs or H2 blocker s for acid suppression in the past year?	PPI, H2 blocker, Both, None
Were the PPIs or H2 blockers recommended or prescribed by a physician?	Yes, No
How many months ago did you start?	0-12 months
Please specify the number of weeks ago you started.	0-4 weeks
Have you taken a PPI or H2 blocker for acid suppression in the past 14 days?	PPI, H2 blocker, Both, None
Are you still taking PPIs or H2 blocker s for acid suppression?	PPI, H2 blocker, Both, None
How long ago did you stop taking PPIs or H2 blockers for acid suppression?	0-12 months
Please specify the number of weeks ago you stopped	0-4 weeks
Please answer the following questions about GI symptoms and use of aspirin for CV prevention	
Did you experience any GI symptoms while taking aspirin for CV prevention?	Yes, No
What do you think caused the GI symptoms?	Activity, Food, Drink, Stress, Aspirin, Other, Not Sure
Did you stop taking aspirin for CV prevention because of GI symptoms?	Yes, No
Please answer the following questions for the past 7 days	

How often have you had difficult getting a good night's sleep because of your symptoms?	Daily, Often, Sometimes, Never
< RDQ for past 7 days>	
<XQS for past 7 days>	
<GSRS for past 7 days>	
Please answer the following questions about yourself	
<HADS>	See questionnaire
<SSAP>	See questionnaire
<SF-8>	See questionnaire
<Morisky>	See questionnaire
Thank you!	

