A burning feeling in the center of the upper stomach?	Did not have, Very mild, Mild, Moderate, Moderately sever, Severe
A pain in the center of the upper stomach?	Did not have, Very mild, Mild, Moderate, Moderately sever, Severe
An acid taste in your mouth?	Did not have, Very mild, Mild, Moderate, Moderately sever, Severe
Unpleasant movement of material upwards from the stomach?	Did not have, Very mild, Mild, Moderate, Moderately sever, Severe
Were you bothered by NAUSEA? (By nausea we mean a feeling of sickness that may lead to retching and vomiting.)	No discomfort at all, minor discomfort, mild discomfort, moderate discomfort, moderately severe discomfort, sever discomfort, very severe discomfort
Did your stomach feel BLOATED? (Feeling bloated refers to swelling often associated with a sensation of gas or air in the stomach.)	No discomfort at all, minor discomfort, mild discomfort, moderate discomfort, moderately severe discomfort, sever discomfort, very severe discomfort

Did your stomach felt BLOATED? (Feeling bloated refers to swelling often associated with a sensation of gas or air in the stomach.)
	
No discomfort at all, minor discomfort, mild discomfort, moderate discomfort, moderately severe discomfort, sever discomfort, very severe discomfort

Did you feel CRAMPS in your stomach/belly?
	
No discomfort at all, minor discomfort, mild discomfort, moderate discomfort, moderately severe discomfort, sever discomfort, very severe discomfort

	

Thinking about your emotions during the episode...
	

Able to focus?
	
NO!!, no??. yes??. YES!!

Alert?
	
NO!!, no??. yes??. YES!!

Angry/frustrated?
	
NO!!, no??. yes??. YES!!

Bored
	
NO!!, no??. yes??. YES!!

Calm/relaxed?
	
NO!!, no??. yes??. YES!!

Difficulty concentrating?
	
NO!!, no??. yes??. YES!!

Enthusiastic?	NO!!, no??, yes??, YES!!
Happy?	NO!!, no??, yes??, YES!!
Irritable?	NO!!, no??, yes??, YES!!
Miserable?	NO!!, no??, yes??, YES!!
Nervous/tense?	NO!!, no??, yes??, YES!!
Quiet/sleepy?	NO!!, no??, yes??, YES!!
Restless?	NO!!, no??, yes??, YES!!
Sad?	NO!!, no??, yes??, YES!!
Overall feeling?	Very bad, Bad, Neutral, Good, Very good
Arousal/energy level?	Very low, Low, Moderate, High, Very high
Please answer these questions about what you did about your episode/	

What did in response to the episode?	Nothing, Change Acitivity, Eat, Drink, Medication, Contact doctor/hospital

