What medication did you take?	PPIs, H2, drink, over-the-counter
What do you think caused the episode?	Nothing, Activity, Food, Drink, Mood, Stress
Thank you!	

Morning Assessment

Text	Response options
ABOUT LAST NIGHT...	
Cigarettes smoked but NOT entered?	0-10
Trouble falling asleep?	NO!!, no??., yes??., YES!!
Slept well?	NO!!, no??., yes??., YES!!
Number of awakenings?	0-20
Since last report	
Did you experience a GI episode?	Yes, No
Thinking about your emotions since your last report...	
Able to focus?	NO!!, no??., yes??., YES!!
Alert?	NO!!, no??., yes??., YES!!
Angry/frustrated?	NO!!, no??., yes??., YES!!
Bored	NO!!, no??., yes??., YES!!
Calm/relaxed?	NO!!, no??., yes??., YES!!

Difficulty concentrating?	NO!!, no??., yes??., YES!!
Enthusiastic?	NO!!, no??., yes??., YES!!
Happy?	NO!!, no??., yes??., YES!!
Irritable?	NO!!, no??., yes??., YES!!
Miserable?	NO!!, no??., yes??., YES!!
Nervous/tense?	NO!!, no??., yes??., YES!!
Quiet/sleepy?	NO!!, no??., yes??., YES!!
Restless?	NO!!, no??., yes??., YES!!
Sad?	NO!!, no??., yes??., YES!!
Overall feeling?	Very bad, Bad, Neutral, Good, Very good
Arousal/energy level?	Very low, Low, Moderate, High, Very high
Thank you!	

Afternoon Assessment

Text	Response options
Since last report	
Did you experience a GI episode?	Yes, No
Where were you most?	Home, Workplace, Other's home, Bar, Restaurant, Vehicle, Outside, Casino, Other
What were you doing?	Working/chores, Inactive/leisure, Interacting with others, Eating/drinking (15 min), Between activities, Other activities
Type of work?	Job, School, House/Personal, Other
Type of inactivity/leisure?	Media, Hanging out, Hobbies, Sports/Exercise, Reading, Waiting, Doing nothing, Other
Type of interaction with others?	Socializing, For business, Household issues, Arguing, Other interaction
What eating or drinking?	Meal, Snack, Caffeinated drink, Non-caffeinated drink, Alcohol

Thinking about your emotions since your last report...	
Able to focus?	NO!!, no??, yes??, YES!!
Alert?	NO!!, no??, yes??, YES!!
Angry/frustrated?	NO!!, no??, yes??, YES!!
Bored	NO!!, no??, yes??, YES!!
Calm/relaxed?	NO!!, no??, yes??, YES!!

Difficulty concentrating?	NO!!, no??, yes??, YES!!
Enthusiastic?	NO!!, no??, yes??, YES!!
Happy?	NO!!, no??, yes??, YES!!
Irritable?	NO!!, no??, yes??, YES!!
Miserable?	NO!!, no??, yes??, YES!!
Nervous/tense?	NO!!, no??, yes??, YES!!

Quiet/sleepy?	NO!!, no??, yes??, YES!!
Restless?	NO!!, no??, yes??, YES!!
Sad?	NO!!, no??, yes??, YES!!

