Overall feeling?	Very bad, Bad, Neutral, Good, Very good
Arousal/energy level?	Very low, Low, Moderate, High, Very high
Thank you!	

Evening Assessment

Text	Response options
Answer the following about the time since your last evening report...	
Since last evening report	
What medications did you take?	Low dose aspirin, Other heart medication, GI medication
Did you visit the doctor or hospital?	Doctor, Emergency room, Hospital
Was it a planned visit?	Yes, No
Are you still in the hospital?	Yes, No
Why did you visit the hospital or doctor?	Heart related problems, GI problems, other
Able to control important things?	NO!!, no??. yes??. YES!!
Able to handle personal problems?	NO!!, no??. yes??. YES!!

Nervous/stressed?	NO!!, no??. yes??. YES!!
Things going your way?	NO!!, no??. yes??. YES!!
Unexpected event upset you?	NO!!, no??. yes??. YES!!
Upset by things out of your control?	NO!!, no??. yes??. YES!!
Since last report	
Did you experience a GI episode?	Yes, No
Where were you most?	Home, Workplace, Other's home, Bar, Restaurant, Vehicle, Outside, Casino, Other

What were you doing?	Working/chores, Inactive/leisure, Interacting with others, Eating/drinking (15 min), Between activities, Other activities
Type of work?	Job, School, House/Personal, Other
Type of inactivity/leisure?	Media, Hanging out, Hobbies, Sports/Exercise, Reading, Waiting, Doing nothing, Other
Type of interaction with others?	Socializing, For business, Household issues, Arguing, Other interaction
What eating or drinking?	Meal, Snack, Caffeinated drink, Non- caffeinated drink, Alcohol
Thinking about your emotions since your last report...	
Able to focus?	NO!!, no??. yes??. YES!!

Alert?	NO!!, no??. yes??. YES!!
Angry/frustrated?	NO!!, no??. yes??. YES!!
Bored	NO!!, no??. yes??. YES!!
Calm/relaxed?	NO!!, no??. yes??. YES!!
Difficulty concentrating?	NO!!, no??. yes??. YES!!
Enthusiastic?	NO!!, no??. yes??. YES!!

Happy?	NO!!, no??. yes??. YES!!
Irritable?	NO!!, no??. yes??. YES!!
Miserable?	NO!!, no??. yes??. YES!!
Nervous/tense?	NO!!, no??. yes??. YES!!
Quiet/sleepy?	NO!!, no??. yes??. YES!!
Restless?	NO!!, no??. yes??. YES!!

Sad?	NO!!, no??. yes??. YES!!
Overall feeling?	Very bad, Bad, Neutral, Good, Very good
Arousal/energy level?	Very low, Low, Moderate, High, Very high

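### The diary's episode-medication item mixes drug class with source of supply, so PPI and H2-blocker use in response to episodes is recorded ambiguously and may be misclassified

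*Protocol*

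**What the plan says.** Appendix D, self-initiated assessment. After an episode the subject is asked what he or she did about it, with the answers "Nothing, Change Acitivity, Eat, Drink, Medication, Contact doctor/hospital". The next item asks which medication was taken and offers "PPIs, H2, drink, over-the-counter". The printed text does not say whether one answer or several may be given.

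Appendix D, evening assessment. The daily medication item offers "Low dose aspirin, Other heart medication, GI medication". The printed morning and afternoon assessments contain no medication question, although Table 3 (section 4.2.2) marks medication usage at all four time points.

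Appendix C, SitePro survey. Class is asked in its own items, with the answers "PPI, H2 blocker, Both, None". A separate Yes/No item asks: "Were the PPIs or H2 blockers recommended or prescribed by a physician".

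Section 1.1 says, of symptoms and their possible influence on treatment, that "use of acid inhibitory drugs and other medications is the focus of the current study". Section 3.1 says of the diary that "the specific questions are listed in Appendix D", so the appendix is where the response options are fixed.

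**The concern.** The answers to a medication item should place each product in one known category. These do not. PPI and H2 are classes, over-the-counter is a route of supply, and drink already stands beside medication as an alternative in the preceding item. No answer names an antacid, and there is no residual class.

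The overlap is not far-fetched, because the survey's own item on physician recommendation foresees PPI or H2-blocker use without one. At stake is one diary variable that bears on a stated focus of the study: which acid-inhibitory drugs subjects take when symptoms occur. If class is not captured on the device, no later analysis can supply it. A coding rule in the statistical analysis plan could say how over-the-counter answers are counted, but not what they contained.

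**Working it through.** The plan gives no figure for this item, so there is none to reproduce. The check has two parts.

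**1. Which answer does each product get?**

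| Product taken for an episode | Answers that fit |
|---|---|
| PPI or H2 blocker, prescribed | Class only |
| PPI or H2 blocker, self-bought | Class, and over-the-counter |
| Antacid, self-bought | Over-the-counter (or drink, if liquid) |
| Any other remedy, self-bought | Over-the-counter |

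The second row is the overlap. Rows two to four share an answer, so over-the-counter alone does not identify a class.

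**2. Is class recorded anywhere else during the three months?**

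- Evening report: one undivided GI medication answer, so any use but not class.
- Printed morning and afternoon reports: no medication question.
- Scheduled reports with elevated symptoms: the note to Table 3 says of subjects that "then they would receive all GI symptoms similar to debriefing of a SI episode". Whether this brings in the medication item is not spelled out. If it does, it brings in the same options.
- Visits: Table 1 has concomitant medication at Visit 1 only. Sections 3.4.1.2 and 3.4.1.3 require nothing beyond the compliance review and, at Visit 3, collection of the device (interviewed subjects apart).

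The item is therefore the only scheduled record of class during follow-up.

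**Possible size.** Let s be the share of PPI/H2 uses for episodes that are self-bought, and q the share of those answered as over-the-counter without the class. Neither is in the documents; both are assumptions.

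Share of PPI/H2 uses missing from the class counts = s × q

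| | s = 0.2 | s = 0.5 |
|---|---|---|
| q = 0 (class always ticked) | 0% | 0% |
| q = 0.5 | 0.2 × 0.5 = 10% | 0.5 × 0.5 = 25% |
| q = 1 (class never ticked if self-bought) | 0.2 × 1 = 20% | 0.5 × 1 = 50% |

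**Bounds from the collected data.** Let N be the true number of PPI/H2 uses and A the number of antacid or other uses answered over-the-counter alone.

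- Class answers recorded: N(1 − sq)
- Over-the-counter alone: Nsq + A
- Counting none of the latter as PPI/H2 gives N(1 − sq), which is too low unless sq = 0.
- Counting all of them gives N(1 − sq) + Nsq + A = N + A, which is too high unless A = 0.

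The truth lies between the two, provided that class answers are correct and no PPI/H2 use was entered as drink.

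**The case against.** The strongest reply is that no bias is demonstrated. Appendix D does not say that the item takes one answer. The evening medication list is printed in the same format, and it works only if several answers are possible, since a subject may take aspirin, another heart medication and a GI drug on one day. If the episode item also takes several, ticking H2 and over-the-counter gives both class and source, and nothing is lost. This stands: the zero in the table is a real possibility, and an undercount cannot be stated as fact.

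A reader might infer three stronger things that the documents do not support.

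- *That the missing antacid answer lowers the PPI/H2 count.* It does not. It makes over-the-counter a mixed category, and counting that whole category as acid suppression would give an overcount.
- *That the definition of Groups 2 and 3 is affected.* Groups are assigned at Visit 1 from the SitePro survey and site review (sections 3.3.3.1 and 3.3.7), and the survey asks class and physician recommendation separately.
- *That the start of acid suppression in Group 2 is missed.* The evening report asks about GI medication since the previous evening report, so first use is recorded; only its class may be unclear.

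It can also be said that the objectives (section 2) speak only of other relevant medications, that section 6.2.2 puts the weight on symptom onset and change in aspirin use, and that the study is exploratory. This limits the importance to one variable. It does not remove the point, because section 1.1 names acid-inhibitory drug use and the survey takes care to record class.

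**Conclusion.** The point holds as a measurement ambiguity. The response options overlap, one of them pools unlike products, and no other scheduled record gives class during follow-up. Class-specific acid-suppressant use in response to episodes is therefore open to misclassification.

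The likely direction is an undercount of PPI/H2 use, conditional on subjects choosing over-the-counter in place of the class. Under the assumed shares the loss is 0% to 50%. The lower end needs several answers to be allowed and the class always ticked. The upper end needs half of the uses to be self-bought and none of those to be given a class. The documents fix neither share, so the range is an illustration, not an estimate.

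Use of any GI medication, its timing by evening report, and group assignment are not called into question. The change is worth making because it is cheap and the lost information cannot be recovered, but the harm is confined to one diary variable.

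**What to change.** - Replace the episode-medication options with drug classes, several answers allowed: PPI; H2 blocker; antacid or alginate; other stomach remedy. State for each that it covers prescribed and self-bought products.
- Drop drink from this item; the preceding item already has it.
- Show the same list in the evening report when GI medication is ticked.
- If source of supply is wanted, ask it as a separate item, as the survey does.
- For answers already collected, report over-the-counter alone as class unknown. Give PPI/H2 use as a lower bound (none of these counted) and an upper bound (all counted). State whether the device allowed one answer or several.

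The cost is a wording change in the device program, plus one short follow-up list in the evening on days with GI medication. The drawback is a break in the item if the change is made after diaries have started. Amendment 2, whose signature appendix is dated 19 June 2008, puts the end of diary enrolment at about 15 June 2008, so by then few new diaries would gain from rewording and the bounded reporting is the main remedy.

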3.3.3.2 Exclusion criteria

- Concomitant treatment with a non-ASA NSAID including a cyclooxygenase-2 (COX-2) selective NSAID. Occasional use of up to 1 day/week is allowed.
- Hospitalised at the time of the survey or EMA entry.
- Planned hospitalisation during the EMA data collection period (3 months).
- Inability to complete the diary daily.

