3.3.6 Discontinuation of subjects from assessment

3.3.6.1 Criteria for discontinuation

Subjects may be discontinued from study at any time. Specific reasons for discontinuing a subject from this study include:

1. Voluntary discontinuation by the subject who is free at any time to discontinue his/her participation in the study without prejudice to further treatment;
2. Severe non-compliance to the CSP as judged by the investigator and/or AstraZeneca;
3. Incorrect enrolment; i.e., enrolment in violation of the inclusion/exclusion criteria;
4. Subjects who are not completing at least 80% of their evening reports, indicating non-compliance with the diary recording requirements of the CSP;
5. If a physician recommends that the subject discontinue use of LDA, the subject will be discontinued from the study;
6. Intake of concomitant medication prohibited by the CSP.

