3.4 Study plan and visit procedures

The study plan outlining visits and procedures is shown below.

Table 1 Study plan

Visit Nos. Assessments	Visit 1 Day 1	Visit 2 Day 45 +/-7 days	Visit 3 Day 90 +/-7 days	Cognitive Interview Visit 3 +45 days
Informed consent	X			
Demographics	X			
Medical/surgical history	X			
Concomitant medication	X			
Inclusion/exclusion criteria	X			
SitePro Survey	X			
Training on ePRO Diary device	X			
Review subject's performance with ePRO device		X	X	
Conduct cognitive interview				X

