Once trained, subjects will be sent into the field to capture data on a daily basis using the ePRO device. Each day the ePRO device will prompt (via an audible alarm) the subject three (3) times each day and administer questions regarding the subject's experience with LDA. In particular, the ePRO device will ask subjects about upper GI symptoms, medication use, and about their daily activities and mood. The ePRO-EMA diary-assessment is outlined in Section 4.2.2, specific questions are listed in Appendix D. Additionally, subjects can make entries into the ePRO device at any time about any discrete episode of UGI symptoms that they experience. Upon making an entry, the device will administer questions about the nature of the episode.

The structure of how the ePro diary device will prompt the subject over the course of a day is depicted below.

Figure 2 ePRO Device daily window schematic

Delay Feature will be available for Morning, Afternoon, Evening Report alarms.

After following these daily procedures, the subjects will put the ePRO device onto a charging device that also contains a modem to transfer data. Each night, the device will automatically (without subject intervention) utilize the modem to transfer the subject's data to a central data server. The investigative site staff will be expected to review subject compliance with EMA procedures utilizing web access to the data on the central server.

Between this and the next visit, the investigative site may be contacted by a Clinical Research Associate (CRA) if individual subjects are not compliant with the EMA procedures.

3.4.1.2 Visit 2

Approximately 45 days after Visit 1, subjects will return for a review of their compliance with the Diary/EMA procedures. During this visit, the investigative site staff will transfer data

from a subject's ePRO device to the central data server. A review of the subject compliance with the Diary/EMA procedures will then be performed utilizing a web access to the data. Subjects who are not complying with procedures will be given feedback, asked if they are experiencing specific problems, and then asked to comply with procedures for the remainder of the EMA period.

Subjects will be subject to the usual clinical care of the investigative site. No procedures beyond the compliance review are required.

Between this and the next visit, the investigative site may be contacted by a CRA if individual subjects are not compliant with the EMA procedures.

3.4.1.3 Visit 3

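### Table 3 schedules medication use at all four diary time points, but Appendix D asks about LDA only in the evening and about NSAIDs nowhere

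*Protocol*

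**What the plan says.** Section 4.2.2, Table 3, carries the row "Medication usage X X X X" for the Morning, Afternoon, Evening and Self-initiated assessments. The row has no asterisk, so unlike GI symptoms and GI coping it does not depend on a positive symptom screen. The section states that the areas are "outlined below and listed in detail in Appendix D". Section 3.4.1.1 says of the three daily prompts that "the ePRO device will ask subjects about upper GI symptoms, medication use, and about their daily activities and mood". Table 3 also marks activities and eating at the Morning assessment.

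The medication items in Appendix D are:

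- **Morning and Afternoon:** none. The Morning form also has no activity or eating item.
- **Self-initiated:** which remedy was taken for the episode (PPI, H2 blocker, drink or over-the-counter product). LDA is not an option.
- **Evening:** a list of "Low dose aspirin, Other heart medication, GI medication", for the time since the previous evening report, with no time of intake.

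No form names NSAIDs. Section 3.3.3.2 excludes concomitant NSAID treatment but adds "Occasional use of up to 1 day/week is allowed". Criterion 6 of Section 3.3.6.1 is "Intake of concomitant medication prohibited by the CSP". In Table 1 the row "Concomitant medication" is marked at Visit 1 only.

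**The concern.** The protocol contradicts itself about what the diary collects, and the contradiction touches a stated objective. Section 2 sets out to record symptoms together with compliance with LDA and other relevant medications. Section 6.2.2 points the GEE models at symptom onset and change in LDA usage. Section 1.1 justifies momentary assessment by the weakness of recall, yet the key exposure is captured by end-of-day recall over a window that lengthens whenever an evening report is missed.

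At stake are three things: whether a symptom came before or after that day's dose or omission, how accurate the adherence figure is, and whether a competing cause of GI symptoms (NSAIDs) is measured at all. A later analysis plan cannot recover answers that the device never asked for.

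**Working it through.** **Item count, Table 3 against Appendix D**

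| Assessment | Table 3 medication row | Any medication item in Appendix D | LDA named | NSAID named |
|---|---|---|---|---|
| Morning | yes | no | no | no |
| Afternoon | yes | no | no | no |
| Evening | yes | yes | yes | no |
| Self-initiated | yes | yes (remedy for the episode) | no | no |
| Total | 4 of 4 | 2 of 4 | 1 of 4 | 0 of 4 |

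The Table 3 footnote sends a subject with elevated symptoms to a debrief like the self-initiated one. That could add the remedy question to a scheduled prompt, but never LDA.

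**Within-day order.** LDA is recorded once a day without a time. When an episode and a dose or omission fall on the same day, nothing in Appendix D orders them, whatever the completion rate.

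**Merged windows.** Criterion 4 of Section 3.3.6.1 sets an 80% floor for evening reports. Over 90 days that is 72 reports and 18 missed. If the misses are isolated, 18 two-day windows cover 36 of 90 days (40%) and 54 one-day windows cover the rest (54 + 36 = 90). In a two-day window one tick cannot separate one dose from two.

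**Size of the adherence error.** The protocol gives no figure to reproduce. Assume that:

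- evening reports are missed independently with probability m;
- a dose is missed with probability q per day, independently of reporting;
- every completed report is counted as one day.

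A window of k days has probability (1−m)m^(k−1) and shows no LDA only if all k doses were missed, probability q^k. Summing over k:

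recorded missed-dose rate = (1−m)q / (1−mq)

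| True q | m = 0.20 (80% completion) | Adherence overstated by | m = 0.10 (90% completion) | Adherence overstated by |
|---|---|---|---|---|
| 5% | 0.040/0.990 = 4.0% | 1.0 point | 0.045/0.995 = 4.5% | 0.5 point |
| 15% | 0.120/0.970 = 12.4% | 2.6 points | 0.135/0.985 = 13.7% | 1.3 points |
| 30% | 0.240/0.940 = 25.5% | 4.5 points | 0.270/0.970 = 27.8% | 2.2 points |

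At 100% completion m = 0 and the recorded rate equals q. A simulation of one million days agrees with the formula: for true adherence of 80% at 80% completion, it gives 83.34% against 83.33%. The values of q and the independence are assumptions.

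**NSAIDs.** Sections 3.4.1.2 and 3.4.1.3 require nothing at Visits 2 and 3 beyond the compliance review and collection of the device (apart from subjects chosen for interview). With no diary item and no medication update, no scheduled procedure after Visit 1 records NSAID use.

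**The case against.** The best defence is that the diary still gives a workable adherence measure. LDA is taken once daily according to the synopsis, so on consecutive evening reports the tick is a usable daily yes/no. Missed reports are visible in the data. An analysis limited to consecutive reports removes the computed bias entirely under the same independence assumption. The protocol does not prescribe a face-value analysis, and Sections 3.4.1 and 7.1 provide compliance follow-up meant to keep completion above the floor. All of this stands, so a reader who infers that adherence is necessarily overstated goes further than the documents allow.

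Three other strong readings also fail:

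- **The models cannot separate cause from consequence.** Only within-day order is lost. Day-to-day order stays recoverable where evening reports are consecutive, and the study is exploratory without hypothesis tests (Section 6.2).
- **PPI and H2 blocker use cannot be allowed for.** The survey asks about current, 14-day and past-year use. Groups 2 and 3 are defined partly by acid suppression, and the episode items, possibly also the conditional debrief, name the class. Only the evening list merges them.
- **Criterion 6 cannot be checked at all.** Usual care at Visits 2 and 3 and source-record review (Section 7.1) may reveal NSAID use. That is incidental rather than systematic, and over-the-counter use could be missed.

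The absence of a none option proves little, because the evening doctor/hospital item also lists no null answer. None of this removes the conflict between Table 3 and Appendix D, restores within-day order, or supplies NSAID data.

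**Conclusion.** The point holds as a contradiction in the protocol's own instrument, with real but limited consequences. Table 3 promises medication use at four time points; Appendix D delivers it at two, and LDA at one.

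The loss of within-day order is certain and needs no assumption. The adherence error is conditional: about 1 to 4.5 points at the 80% floor for missed-dose rates of 5% to 30%, about half that at 90% completion, and none at 100% or when only consecutive reports are used. It rests on independent misses. If subjects tend to miss doses and reports together, the error would be larger, by an amount the documents do not allow to be sized. NSAID exposure during the diary period is unmeasured, and the 1 day/week limit and criterion 6 are not systematically checked.

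**What to change.** Reconcile Table 3 and Appendix D:

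1. Add a short medication item that includes LDA (taken since the last report, yes/no) to the Morning and Afternoon forms, and the missing activity and eating items to the Morning form. This places a dose within a prompt window; clock times and dose counts are optional.
2. Make the evening LDA item ask about each day since the last completed evening report. This removes the merged windows.
3. In the evening list, show PPI, H2 blocker, antacid/over-the-counter and NSAID/pain reliever separately, alongside LDA and other heart medication.
4. In Table 1, add a concomitant-medication update at Visits 2 and 3, which already take place.

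These are measurement changes only and alter no clinical rule. The cost is a device configuration change, a few extra taps a day and a short update at two existing visits. Asking about LDA more often may act as a small reminder and so affect the behaviour under observation. The benefit reaches only diary data collected after the change. Amendment 2 puts the end of diary-phase enrolment at about 15 June 2008, so for data already collected the report should state the limits on within-day order and NSAID exposure.
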